### 2.3 PHARMACOKINETIC OBJECTIVE

The PK objective for this study is to characterize the FHTR2163 PK profile on the basis of the following endpoint:

Serum and aqueous humor concentration of FHTR2163 at specified timepoints

The exploratory PK objective for this study is as follows: To evaluate potential relationships between drug exposure and the safety and efficacy of FHTR2163 on the basis of the following endpoints:

- Relationship between serum and/or aqueous humor concentration or PK parameters for FHTR2163 and efficacy endpoints
- Relationship between serum and/or aqueous humor concentration or PK parameters for FHTR2163 and safety endpoints

### 2.4 IMMUNOGENICITY OBJECTIVE

The immunogenicity objective for this study is to evaluate the immune response to FHTR2163 on the basis of the following endpoint:

 Prevalence of serum ADAs at baseline and incidence of serum ADAs during the study

The exploratory immunogenicity objective for this study is to evaluate potential effects of serum ADAs on the basis of the following endpoint:

Relationship between ADA status and efficacy, safety, or PK endpoints

### 2.5 BIOMARKER OBJECTIVES

The exploratory diagnostic biomarker objective for this study is to evaluate the efficacy of FHTR2163 as defined in the primary efficacy objective (see Section 2.1.1) in carriers versus non-carriers of the HtrA1 AMD risk variant rs10490924.

The exploratory biomarker objective for this study is to identify and/or evaluate biomarkers that are predictive of response to FHTR2163, are associated with rate of progression to a more severe disease state, are associated with susceptibility to developing adverse events, can provide evidence of FHTR2163 activity, or can increase the knowledge and understanding of disease biology, on the basis of the following endpoints:

 Relationship between biomarkers in blood and aqueous humor (listed in Section 4.5.8) and efficacy, safety, PK, immunogenicity, or other biomarker endpoints  Relationship between retinal imaging measures (e.g., FAF, SD-OCT, optical coherence tomography angiography [OCT-A]) and efficacy, safety, PK, immunogenicity, or other biomarker endpoints

### STUDY DESIGN

### 3.1 DESCRIPTION OF THE STUDY

This is a Phase II, multicenter, randomized, single-masked, sham-controlled study evaluating the safety, tolerability, and efficacy of 20 mg FHTR2163 dose administered Q4W or Q8W by ITV injections for approximately 76 weeks, in patients with GA secondary to AMD. Approximately 360 patients (144 patients in FHTR2163 Q4W arm, 72 patients in FHTR2163 Q8W arm, and 144 patients in pooled sham arm) will be enrolled in the study at approximately 77 investigational sites in the United States. Site investigators will be qualified ophthalmologists.

[figure not shown]
The study will consist of the following:

- Screening period of up to 120 days, divided into a prebaseline screening period (Day –120 to Day –31) and a baseline screening window (Day –30 to Day –1)
- Treatment period of up to 68 weeks (Day 1 to Week 68 for the Q4W treatment arms and Day 1 to Week 64 for the Q8W treatment arms)
- Primary analysis timepoint visit (Week 72)
- Final study visit (Week 76)

The duration of the study is approximately 76 weeks after the last patient is randomized to the study.

Figure 1 presents an overview of the study design. Schedules of activities are provided in Appendix 1 and Appendix 2.

Figure 1 Study Schema

GA = geographic atrophy; N = number; Q4W = every 4 weeks; Q8W = every 8 weeks.

To be eligible for the study, patients must satisfy all eligibility criteria (see Section 4.1) at both the screening visit(s) and the Day 1 visit (i.e., day patient is enrolled and study drug is administered).

One essential eligibility criterion is that patients will be required to have two FAF images, a prebaseline image and a baseline image performed on a Heidelberg platform obtained at a minimum of ~3 months (84 days) and maximum of ~11 months (336 days) prior to the baseline screening visit. The prebaseline and baseline FAF images may be obtained in two different approaches as illustrated in Figure 2 and described below.

## No Preexisting FAF Image

Patients who do not have a preexisting FAF image available will have an FAF obtained along with all other prebaseline assessments listed in Appendix 1 and Appendix 2 to assess eligibility. This FAF image will be designated as the prebaseline FAF image. If the prebaseline FAF image is ungradable by the reading center, a repeat FAF image needs to be obtained within 30 days. Up to an additional 7 business days may be permitted for exceptional circumstances after consultation with and approval by the Medical Monitor. If prebaseline eligibility criteria for the FAF image (see Section 4.1) are met, the patient will enter the 90 (+30) day prebaseline screening period starting from the date the FAF image was obtained. The patient will then return to the clinic during the baseline screening window (Day –30 to Day –1) to perform the screening assessments (except for keratometry), including the baseline FAF image (see Appendix 1 and Appendix 2 and Figure 2).

### Preexisting FAF Image

Patients with a preexisting FAF image that was obtained on a Heidelberg platform and was obtained 84–336 days prior to the baseline screening visit may have the preexisting FAF image designated as the prebaseline FAF image, and the patient may proceed directly to the baseline screening window (Day –30 to Day –1) to obtain the baseline FAF image along with the other screening assessments (see Figure 2).

Any preexisting near infrared (NI) image obtained 84–336 days prior to the baseline screening visit should also be sent to the central reading center. Preexisting NI images are not necessary for eligibility and absence of a preexisting NI image(s) does not exclude a patient from screening.

If patients have more than one preexisting FAF/NI image (obtained 84–336 days prior to the baseline screening visit), all such images should be sent to the central reading center.

In the event the preexisting FAF image is deemed not gradable by the central reading center or the measured GA lesion size is smaller than required (< 2.54 mm^2), the FAF image obtained during the baseline screening window will be considered the prebaseline image. If all other eligibility criteria are met (see Section 4.1), the patient will be allotted

an additional 90 (+30) days from the date that FAF image was obtained to return to the clinic. The patient then will repeat the baseline screening window assessments (except for HtrA1 genotyping whole blood sample and keratometry), including the baseline FAF (see Figure 2).

Prebaseline and baseline screening assessments may be completed on separate days provided that all assessments are captured within the prebaseline screening period (Day –120 to Day –30) or baseline screening window (Day –30 to Day –1), respectively. The baseline screening window may be extended for up to 7 business days for exceptional circumstances after consultation with and approval by the Medical Monitor. All prebaseline and baseline screening images (see Appendix 1 and Appendix 2 for details of images required) must be received and evaluated by the central reading center prior to the Day 1 visit.

Prebaseline FAF (via Heidelberg platform) and NI images a Yes No Baseline screening window Prebaseline screening period (D -30 to D -1) (D -120 to D -31) Perform baseline FAF Perform FAF on the first day of the screening period (this FAF will be considered as the prebaseline FAF) **FAF** FAF Gradable Not gradable or GA lesion size eligibility not met Baseline screening Prebaseline screening period window (D -120 to D -31) (D -30 to D -1) Prior baseline FAF from screening will be considered as the prebaseline FAF Perform baseline FAF Repeat baseline screening window (D - 30 to D - 1)Repeat all screening assessments (except for HtrA1 genotyping whole blood sample and keratometry) including baseline FAF If eligible, proceed to Day 1

Figure 2 Prebaseline Image Collection Flowchart

FAF = fundus autofluorescence; GA = geographic atrophy; HtrA1 = high-temperature requirement A1; NI = near infrared.

a Any preexisting NI image obtained 84–336 days prior to the baseline screening visit should also be sent to the central reading center. However, preexisting NI images are not required for eligibility.

Patients who fail screening may be eligible for rescreening up to three additional times during the enrollment period of the study. At rescreening, all screening visit assessments will be performed except for the whole blood sample for HtrA1 genotyping assay and keratometry, provided that a valid HtrA1 risk-variant carrier status result is available.

Eligible patients will be administered study drug or sham control on Day 1. Only one eye will be chosen as the study eye. If both eyes are eligible to become the study eye, the

eye with the worse visual function as determined by the investigator and the patient will be the study eye. If both eyes have the same visual function, the eye with the larger area of GA lesion will be selected as the study eye.

Eligible patients will be randomized in a 2:1:1:1 ratio such that approximately 144 patients will receive study drug treatment Q4W, 72 patients will receive sham-control treatment Q4W, 72 patients will receive study drug treatment Q8W, and 72 patients will receive sham-control treatment Q8W. Patients receiving Q4W dosing will receive a total of 18 treatments and patients receiving Q8W dosing will receive a total of 9 treatments.

Randomization will be stratified by HtrA1 risk-variant carrier status (HtrA1 risk-variant carrier vs. HtrA1 risk-variant non-carrier), baseline GA lesion size (<9.0 mm² vs. ≥9.0 mm²), and annualized prebaseline GA progression rate (<1.9 mm²/yr vs. ≥1.9 mm²/yr). HtrA1 risk-variant carriers and HtrA1 risk-variant non-carriers may be enrolled in either FHTR2163 or sham-control arms.

After randomization on Day 1, patients will be administered the first ITV injection of FHTR2163 or sham control by the investigator. If a site has an unexpected issue (e.g., unable to assign the study kit), with the Medical Monitor's permission, the patient's first study treatment may be administered within 3 working days of the Day 1 visit. The following assessments will be repeated on the day of the study treatment: slit lamp examination, indirect ophthalmoscopy, and pre- and post-treatment intraocular pressure (IOP) measurement (and recorded on the Day 1 electronic Case Report Form [eCRF]).

Subsequent study treatment visits will be scheduled Q4W or Q8W relative to the Day 1 visit date. Study treatment should not occur earlier than 22 days after the previous treatment. Missed study treatments will not be made up.

At the subsequent visits, patients will have safety evaluations performed by the investigator prior to receiving study drug or sham control. Patient self-administered anti-microbials pre- and post-injection may be used at the investigator's discretion. Patients will be educated as to signs and symptoms of post-injection adverse events and instructed to contact the investigator at any time if they have any health-related concerns. All assessments for a scheduled visit will be performed on the same day, (with the exception of assessments performed during the prebaseline screening period or baseline screening window, which may be performed at any time during the 90-day or 30-day time frame, respectively). After the Day 1 visit, if a patient misses a study visit when ocular images are scheduled to be taken (see Appendix 1 and Appendix 2), the images must be obtained at the next scheduled visit.

Patients who are prematurely discontinued from study treatment (but have not withdrawn consent) will be encouraged to undergo as many scheduled visits as possible with emphasis on completing Week 72 visit.

Patients discontinued from the study prior to completion will be asked to return for an early termination visit after a minimum of 30 days have elapsed following the final study treatment for monitoring of adverse events and the early termination visit assessments. Early termination visits not completed after 6 months following the last treatment will be considered as "loss of follow-up" when appropriate.

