# 4.6 TREATMENT, PATIENT, STUDY, AND SITE DISCONTINUATION

# 4.6.1 Study Treatment Discontinuation

Patients must permanently discontinue study treatment if they experience any of the following:

- Any medical condition that the investigator or Sponsor determines may jeopardize the patient's safety if he or she continues to receive study treatment
- Investigator or Sponsor determination that treatment discontinuation is in the best interest of the patient
- Pregnancy
- Unacceptable toxicity
- Any event that meets treatment discontinuation criteria defined in Table 1 in Section 5.1.5.

The primary reason for study treatment discontinuation should be documented on the appropriate eCRF.

Patients withdrawn from the study prior to completion will be asked to return for an early termination evaluation after a minimum of 30 days following his or her final study treatment for monitoring of adverse events and assessments listed for the early termination visit (see Appendix 1 and Appendix 2). The reason for the discontinuation should be recorded on the appropriate eCRF. Discontinued patients will not be replaced or allowed to re-enter the study.

Patients who discontinued treatment will not be allowed to re-start the study treatment. However, they should be strongly encouraged to stay in the study and undergo as many scheduled visits as possible.

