# 4.6.2 Patient Discontinuation from the Study

Patients discontinued or withdrawn from study will return to the clinic for a study discontinuation visit after a minimum of 30 days following his or her final study treatment (see Appendix 1 and Appendix 2).

Patients have the right to voluntarily withdraw from the study at any time for any reason. In addition, the investigator has the right to withdraw a patient from the study at any time.

Reasons for patient discontinuation from the study may include, but are not limited to, the following:

- Patient withdrawal of consent
- Study termination or site closure
- Adverse event
- Loss to follow-up
- Patient non-compliance, defined as failure to comply with protocol requirements as determined by the investigator or Sponsor

Every effort should be made to obtain a reason for patient discontinuation from the study. The primary reason for discontinuation from the study should be documented on the appropriate eCRF. If a patient requests to be withdrawn from the study, this request must be documented in the source documents and signed by the investigator. Patients who withdraw from the study will not be replaced.

If a patient discontinued the study but has not withdrawn the informed consent, the site should make every effort to continue to follow up on serious adverse events, deaths, and adverse events of special interest in these patients.

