- Patients who have an eligible preexisting FAF image may directly enter in the 30-day baseline screening window (see Figure 2). The preexisting FAF will be considered the prebaseline FAF. See Section 4.1 for GA lesion eligibility criteria. Baseline screening activities may be completed across more than one visit if necessary.
- c After completing the study's last visit (Week 76), eligible patients will have the option to enroll in an open-label extension study (GR42558) and receive FHTR2163 injections. The Week 76 visit will serve as the final visit for this study (GR40973; GAllego) and the first (Day 1) visit for Study GR42558. Patients who do not enter Study GR42558 will be contacted 7–10 days after the last visit by a follow-up call to elicit reports of any decrease in vision, eye pain, unusual redness, or other new ocular symptoms in the study eye.
- d For patients who discontinue early from the study, early termination assessments will be performed after minimum of 30 days have lapsed following the final study treatment.
- e The Informed Consent Form needs to be signed and documented only once during prebaseline screening or screening visit.
- f Significant medical and surgical history, including chronic and ongoing conditions (e.g., trauma, cancer, cardiovascular, and ophthalmic history), and tobacco use, surgeries, cancer history, reproductive status, and all medications (e.g., prescription drugs, over-the-counter drugs, vaccines, herbal or homeopathic remedies, nutritional supplements) used by the patient within 7 days prior to Day 1 visit.
- g Demographic data will include age, sex, and self-reported race/ethnicity.
- h Historical ocular images are defined as FAF and SD-OCT images of both eyes obtained up to 5 years prior to the baseline screening window, excluding those used to evaluate prebaseline FAF. Historical ocular images may be collected and submitted any time after enrollment into the study. This assessment is required only for patients who have historical images available.
- Prebaseline FAF and NI images from patients must have been obtained on a Heidelberg platform 84–336 days prior to screening (Day –30 to Day –1). If both eyes have the potential to be eligible for the study, FAF and NI images from both eyes should be sent to central reading center.

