- If the preexisting FAF image is not gradable or the total GA lesion size is smaller than the required (<2.54 mm²), the FAF image obtained during the baseline screening window will be considered as the prebaseline image. If all other eligibility criteria are met (see Section 4.1), the patient will return to clinic for a repeat screening visit 90 (+ 30) days from the date of when the prebaseline image was obtained. During the repeat 30-day baseline screening window, all screening visit assessments will be performed except for HtrA1 genotyping whole blood sample and keratometry.
- k On Day 1, contact IWRS for study drug kit assignment after all assessments are performed.
- To be performed if clinically indicated.
- m Vital signs consist of measurements of respiratory rate, pulse rate, and systolic and diastolic blood pressures while the patient is in a seated position after resting for 5 minutes, and temperature.
- n For a detailed description of sample collection, see the laboratory manual.

- Collect and perform urine pregnancy test for women of childbearing potential, including those who have had tubal ligation, at each study treatment visit. If positive, collect a serum pregnancy sample and forward to central laboratory for testing; if the serum pregnancy test is positive, do not administer the study treatment.
- P At screening, collect serum pregnancy sample for women of childbearing potential, including those who have had tubal ligation. If positive, record the patient as a screen fail. At early termination visit, collect the serum pregnancy sample and forward to the central laboratory for testing.
- In case of Grade >0 non-infectious intraocular inflammation, contact the Medical Monitor to discuss case. An additional serum ADA and PK sample should be collected as close as possible to the time of diagnosis. Consider performing CFP/FA (Appendix 13; widefield CFP/FA or standard CFP/FA with peripheral sweeps is preferred), SD-OCT, and uveitis lab workup as clinically indicated. Additionally, consider treatment with corticosteroids if appropriate, based on the individual patient presentation and comorbidities (e.g., diabetes, systemic hypertension), and consider referring patient to a uveitis specialist and/or rheumatologist, per clinical judgment.
- Perform assessment prior to dilating the eyes.

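### The 30-day minimum before early termination assessments exceeds the 28-day Q4W interval, so a Q4W patient who leaves undosed at an on-time dosing visit without FAF must come back for the final image, while a Q8W patient need not

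*Combined protocol and SAP*

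**What the plan says.** The 30-day minimum appears in five places, with no exception for either schedule:

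- Section 3.1: patients who leave the study are "asked to return for an early termination visit after a minimum of 30 days have elapsed following the final study treatment".
- Section 4.6.1: the ET evaluation takes place "after a minimum of 30 days following his or her final study treatment".
- Section 4.6.2: "Patients discontinued or withdrawn from study will return to the clinic for a study discontinuation visit after a minimum of 30 days".
- Footnote d of Appendix 1 (Q4W) and of Appendix 2 (Q8W): "early termination assessments will be performed after minimum of 30 days have lapsed following the final study treatment".

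On visit timing, Section 3.1 states: "Subsequent study treatment visits will be scheduled Q4W or Q8W relative to the Day 1 visit date". Both appendices give every week visit a ±5-day window. Section 3.1 adds: "Study treatment should not occur earlier than 22 days after the previous treatment".

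After baseline, both appendices schedule FAF at Weeks 24, 48 and 72 and at the ET visit. At unscheduled visits FAF carries footnote l: "To be performed if clinically indicated". BCVA is marked at every visit.

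Section 3.1 also sets an upper limit: "Early termination visits not completed after 6 months following the last treatment will be considered" lost to follow-up, qualified by a statement that this applies when appropriate.

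**The concern.** The ET visit is timed from the last dose, not from the date of leaving. A Q4W patient who announces at an on-time dosing visit that they are leaving is in the clinic at day 28, and the ET assessments may not start before day 30. Unless FAF happens to be due that day, the final image needs a second trip from someone who has just decided to stop coming. A Q8W patient in the same position is at day 56 and can be imaged on the spot.

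FAF provides the primary endpoint, and Section 6.4.1 bases the primary analysis on whatever data exist through Week 72, without imputation. For a patient who leaves before Week 24, the ET FAF is normally the only possible post-baseline GA area. Because sham is pooled over both schedules, the share of patients on the 28-day schedule is 100% against 50% in the Q4W comparison and 0% against 50% in the Q8W comparison. The chance of obtaining a final image can therefore differ between the groups compared.

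**Working it through.** **Inputs from the protocol.** ET minimum 30 days (3.1, 4.6.1, 4.6.2, footnote d). Intervals 28 and 56 days, windows ±5 days, minimum 22 days between doses (3.1, Appendices 1 and 2). Arms of 144 Q4W active, 72 Q8W active and 144 pooled sham, of whom 72 are on Q4W (3.1). Dropout 15% by Week 72 (6.1).

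**Assumed inputs, not in the protocol.** Half of leavers leave at a scheduled visit; 30-50% of those told to return do not; leaving is equally likely at each dosing visit; how visit dates scatter within the window.

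**The plan's own figure.** The protocol gives no estimate for this point. The sample size that carries the 15% dropout reproduces to within one patient: a 0.56 mm² difference, SD 1.82 mm², two-sided 20% level and 80% power need 96 evaluable per group; 96/0.85 = 113 against the stated 114; 114 × 5/2 = 285. Nothing below changes it.

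**Step 1: gap from last dose to leaving visit.** Gap = interval + (d2 − d1), with each offset between −5 and +5.

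- Q4W: 28 ± 10 = 18 to 38 days; on time 28, which is 2 short of 30.
- Q8W: 56 ± 10 = 46 to 66 days; always at least 30.

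**Step 2: share of Q4W gaps under 30 days.**

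- On time: 100%.
- Uniform offsets: of 11 × 11 = 121 pairs, d2 − d1 ≥ 2 in 9 + 8 + … + 1 = 45, so 76/121 = 63% fall short. Dropping the 10 pairs with a gap under 22 days leaves 66/111 = 59.5%.
- Offset SD of 1, 2 or 3 days (with the 22-day floor): 86%, 70%, 64%.

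**Step 3: visits where FAF is taken anyway.** Q4W has 17 dosing visits after Day 1 (Weeks 4 to 68). FAF is due at two of them (Weeks 24 and 48), leaving 15/17 = 88%. The share with no FAF that day is 88% on time and 0.595 × 15/17 = 53% with uniform scatter. If 10-20% had also missed the previous dose (assumed), these fall to 79-71% and 47-42%.

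**Step 4: final images lost.** Q4W-schedule leavers: 0.15 × 144 = 21.6 on active and 0.15 × 72 = 10.8 in pooled sham.

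| | Q4W active | Pooled sham | Q8W active |
|---|---|---|---|
| On time: leavers × 0.5 × 15/17 × (0.3 to 0.5) | 2.9-4.8 | 1.4-2.4 | 0 |
| Uniform: the same × 0.595 | 1.7-2.8 | 0.9-1.4 | 0 |

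**Step 5: patients left with no post-baseline GA area.** Only 5 of the 17 dosing visits (Weeks 4 to 20) precede Week 24.

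- Q4W active, on time: 21.6 × 0.5 × 5/17 × (0.3 to 0.5) = 1.0-1.6; uniform (× 0.595), 0.6-0.9.
- Pooled sham: half of that, 0.5-0.8 on time and 0.3-0.5 uniform.

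**Step 6: the six-month limit.** A patient who stops dosing at Week 20, stays in the study as 3.1 and 4.6.1 encourage, and leaves at Week 56 is 36 weeks past the last treatment, already beyond the limit.

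**The case against.** The rule is the same for everyone and the protocol does not contradict itself. The minimum has a stated purpose, adverse event monitoring, and day 30 falls just after the 28-day adverse event reporting period in Section 5.3.1. One visit after that period is a defensible choice. This stands, and it is the reason to keep that visit rather than replace it with a looser contact.

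A reader might infer that the obstacle falls on the whole Q4W active arm and on nobody in the Q8W active arm. The protocol does not support that. A Q8W patient who leaves at Day 8, at the follow-up call about 14 days after a dose, or between visits soon after a dose also waits until day 30, and a dose given on the day of leaving restarts the clock on either schedule. A Q4W patient who is late, missed the previous dose or had already stopped treatment can meet the rule. The contrast holds only for leaving undosed at a scheduled dosing visit after receiving the previous dose.

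A Q4W patient who gives notice can also be booked 2-5 days late, within the window, and seen at day 30-33 if the last visit was on target. That helps only when the intention is known beforehand.

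It is also tempting to read each lost image as a patient who adds nothing on GA change. Those who leave after Week 24 would normally already have a Week 24 or Week 48 FAF. BCVA is done at every visit, so the loss is mainly FAF and NI.

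The six-month wording might be read as mislabelling known withdrawals. The qualifier in 3.1, and the requirement in 4.6.2 to record the primary reason for discontinuation, largely cover this.

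**Conclusion.** The point holds in a narrow form. For patients who leave undosed at a scheduled dosing visit without FAF, having received the previous dose, same-day ET imaging is ruled out on Q4W in 100% of cases with on-time visits and in about 60-63% with uniform scatter. It is never ruled out on Q8W.

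The size is small: about 2-5 final images on Q4W active, half that in pooled sham, and none on Q8W active by this route. About 1-2 Q4W active patients and fewer than one pooled sham patient would have no post-baseline GA area. Apart from the 15% dropout, the inputs to these counts are assumptions.

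A reader might go on to infer that the primary estimate is biased. The documents do not support that: how an off-schedule ET FAF enters the mixed model, and who is in the modified intent-to-treat population, are left to the Data Analysis Plan, and Section 6.4 plans sensitivity analyses for missing data. Neither the direction nor the amount of any bias can be derived. What remains is an avoidable, schedule-dependent gap in primary-endpoint imaging, worth a cheap improvement in wording.

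**What to change.** In Sections 3.1, 4.6.1 and 4.6.2 and in footnote d of Appendices 1 and 2, state that the imaging already listed for the ET visit (FAF and NI), with any other ET efficacy assessments not already done that day, is obtained at the visit at which the patient leaves, whatever the time since the last dose. Leave the existing ET visit, with its 30-day minimum, in place for adverse event monitoring.

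As a minor point, reconcile the six-month wording in 3.1 with the requirement in 4.6.2 to record the actual reason for discontinuation.

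The cost is amendment wording in five places, with no new type of assessment. A few patients may be imaged twice, and some final images will be taken slightly earlier than under the present rule.
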